4.2. Measures to minimise bias

The following measures will be taken in order to minimise bias:

- Analysis of samples for PK and PD will be performed in a specific central laboratory to minimise the variability of measurements.
- Screening for participants with mIDH1 will be performed based on a central evaluation with clinically validated diagnostic test.
- Evaluation of anti-tumour efficacy endpoints will be based on an IRC.
- QoL questionnaires will be completed by the subject independently of the study personnel.

4.3.1.2. Packaging and Labelling

Ivosidenib will be provided as 60-count bottles of 250 mg tablets. At each D1 of each cycle, subject will receive one small box containing one bottle.

4.3.1.3. Blinding Systems

This study is an open-label study. No blinding measures will be taken.

4.3.2. IMP management

IMP receipt, dispensing according to the experimental design of the study (for the description of dispensing methods, refer to [Section 6.2](#)), accountability and collection are the responsibility of the Investigator and/or pharmacist of the medical institution. All these actions have to be done in RTSM as explained in the training video embedded in RSTM.

The recommended storage conditions and expiry (where required) are stated on the product label.

All investigational products must be stored in a secure, limited-access location and may be dispensed only by the Investigator or by a member of the staff specifically authorized by the Investigator. IMP management will be verified on a regular basis by the study monitor.

The Investigator and/or the pharmacist of the medical institution and/or a designated person from their study team must enter and complete in real time in RTSM and all the documents provided by the Sponsor concerning IMP management (refer to pharmacy manual).

The Investigator and/or the pharmacist of the medical institution should only use the IMP provided for the participants involved in the study.

All defects or deterioration of IMPs or their packaging are to be reported to the study monitor. The Investigator will notify the monitor of all complaints reported by a participant (change of taste, appearance, etc.).

Destruction of the IMP is the responsibility of the Sponsor and/or the Investigator and/or the pharmacist of the medical institution.

Remaining treatments (used and unused IMPs) will subsequently be collected and stored according to the local procedures and requirements, by the person responsible for the IMP management. Used IMPs will be collected by the center at the time of preparation / administration along with the other wastes to be destroyed according to local routines.

In the event of anticipated return of IMPs to the Sponsor (batch recall), the Sponsor will prepare an information letter intended for the Investigator and/or pharmacist of the medical institution. This letter will be sent by the person locally responsible for the study to each study centre. On receipt of the letter, the Investigator and/or the pharmacist will identify the participants in possession of the IMP at the moment the incident becomes known, by using RTS or an equivalent document and will contact them immediately.

Study Treatment Storage

Ivosidenib tablets must be stored according to the package label.

All study treatment products must be stored in a secure, limited-access location and may be dispensed only by the Investigator or by a member of the staff specifically authorized by the Investigator.

IMP receipt, dispensing according to the experimental design of the study (for the description of dispensing methods, refer to [Section 6.1.1](#)), accountability and collection are the responsibility of the Investigator and/or pharmacist of the medical institution. All these actions have to be done in RTSM as explained in the training video embedded in RSTM or user manual or pharmacy manual.

The IMP should be stored in a secure area with restricted access. Specific storage conditions, if any, are mentioned on IMP labelling and are detailed in Investigator's brochure.

IMP management will be verified on a regular basis by the study monitor.

The Investigator and/or the pharmacist of the medical institution and/or a designated person from their study team must enter and complete in real time in RTSM and all the documents provided by the Sponsor concerning IMP management (refer to pharmacy manual).

The Investigator and/or the pharmacist of the medical institution should only use the IMP provided for the participants involved in the study.

All defects or deterioration of IMPs or their packaging are to be reported. The Investigator will notify the monitor of all complaints reported by a participant (change of taste, appearance, etc.).

Destruction of the IMP is the responsibility of the Sponsor and/or the Investigator and/or the pharmacist of the medical institution

4.3.3. Management of blinding systems

Not applicable.

4.3.4. Method of assigning subjects to treatment

Only subjects who meet all study eligibility criteria will be received ivosidenib orally.

4.3.5. Study treatment preparation and administration

Daily treatment with ivosidenib will begin on C1D1; clinical observations will be conducted over 6 hours following the first dose of study treatment on C1D1. Dosing is continuous; there are no planned inter-cycle rest periods. Subjects should be instructed to take their QD dose at approximately the same time each day.

Subjects should be instructed to swallow tablets whole and do not chew the tablets. Subjects may take ivosidenib with or without food. Subjects should be advised that if ivosidenib tablets are taken with food, the subject should avoid grapefruit or grapefruit products and avoid consuming a high-fat meal. Please refer to examples of low-fat and high-fat meals in [Appendix 11](#).

If the subject forgets to take the daily dose, then they should take ivosidenib within 12 hours after the missed dose. If more than 12 hours have elapsed, then that dose should be omitted, and the subject should resume treatment with the next scheduled dose.

Subjects will continue to receive best supportive care throughout the study.

Subjects may continue with their study treatment until disease progression, development of unacceptable toxicity, confirmed pregnancy, death, withdrawal of consent, the subject is lost to follow-up, or the Sponsor ends the study, whichever occurs first. Upon radiographic disease progression, PIs, with consult from the Sponsor, may keep the subjects on ivosidenib after the disease progression provided the subject is clinically benefitting and there is no contraindication to continuing treatment beyond progression.

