6. TREATMENT OF PARTICIPANTS

6.1. IMPs administered

Ivosidenib will be administered orally at a dose of 500 mg (provided as 250 mg strength tablets).

Each day, the subject will take 2 tablets of 250 mg ivosidenib at the same time, preferably in the morning, in fasting or non-fasting conditions.

For treatment dose adaptations due to toxicities, please refer to [Section 8.10](#).

All the IMP tracking are managed in RTSM in real time. The procedures to be followed by the Investigator or authorised person are detailed in the training video embedded in RSTM or user manual.

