6.3.2. Concomitant therapy requiring careful monitoring

Concomitant use of drugs with a potential QT prolongation should be avoided and replaced with alternative treatments. If this is not possible, subjects receiving these drugs should be adequately monitored.

These medications include but are not limited to:

- Fluoroquinolones such as ciprofloxacin and moxifloxacin
- Azole antifungals such as fluconazole and posaconazole
- Serotonin (5-HT₃) antagonists such as granisetron and ondansetron

Other examples of drugs known to prolong the QT interval are listed in [Appendix 9](#).

Systemic administration of moderate or strong CYP3A4 inhibitors ([Appendix 6](#)) requires careful monitoring of the QTc.

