6.3.4. Drug-drug interactions

Ivosidenib is mainly metabolized by CYP3A4 and, therefore, subjects should not use strong CYP3A4 inducers ([Appendix 6](#)) during treatment with ivosidenib.

Ivosidenib clinical trials and physiologically based pharmacokinetic (PBPK) simulations have shown that ivosidenib plasma concentrations increase with co-administration of a strong or moderate CYP3A4 inhibitor ([Appendix 6](#)), and increased ivosidenib plasma concentrations may increase the risk of QTc prolongation. Therefore, alternative therapies that are not strong or moderate CYP3A4 inhibitors should be considered during treatment with ivosidenib. If concomitant use of strong or moderate CYP3A4 inhibitors is unavoidable, subjects should be monitored for increased risk of QTc prolongation.

Ivosidenib is an inducer of human CYP3A4/5 and may also induce CYP2B6, CYP2C8, and CYP2C9. Therefore, medications of sensitive CYP3A4 substrates with a narrow therapeutic window ([Appendix 6](#)) should be avoided unless the subject can be transferred to other medications prior to enrolling. Consider alternative therapies that are not sensitive substrates of CYP2C9 (eg, phenytoin, warfarin). Monitor coagulation values more frequently in subjects receiving warfarin (a CYP2C9 substrate) during initiation or discontinuation of ivosidenib.

Ivosidenib is an inhibitor of OAT3. A PBPK simulation predicted an increase (< 30%) in the AUC of a sensitive OAT3 substrate, suggesting that the potential for clinically relevant drug interactions due to the inhibition of OAT3 appears to be low.

Coadministration of ivosidenib may decrease the concentrations of hormonal contraceptives. Consider alternative methods of contraception in subjects receiving ivosidenib.

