8.11. Potential Risks

8.11.1. Guidelines for Management of QT Prolongation

The discussion of the emergency management of Torsades de pointes and its hemodynamic consequences is beyond the scope of this guideline.

Events of QTcF prolongation as defined in [Section 8.6](#) should be reported as AEs of special interest (AESIs) to the Sponsor within 24 hours, according to expedited reporting procedures.

The following are guidelines for the management of AEs of special interest based on the ivosidenib non-clinical and clinical safety findings in subjects with solid tumors to date.

Prolongation of QTcF interval has been observed in monkeys at relatively high doses of ivosidenib and has been identified as an expected risk of treatment with ivosidenib (see the Investigator's Brochure).

Subjects may be at increased risk for the development of QT prolongation when treated with ivosidenib in combination with fluoroquinolones, azole antifungal agents, or serotonin (5-HT₃) antagonists. Investigators need to be vigilant; refrain from administering concomitant medications associated with QT prolongation and if no other therapeutic options are available, monitor subjects receiving study treatment with the combination of these drugs, and evaluate ECG and electrolytes (including potassium, magnesium, and total calcium) particularly in subjects presenting with nausea, vomiting, or diarrhea. Systemic administration of a moderate or strong CYP3A4 inhibitor requires careful monitoring of QTcF.

Subjects who experience prolongation of the QTcF interval to > 480 msec (CTCAE Grade ≥ 2) while receiving study treatment, should be promptly evaluated for causality of the QTcF prolongation and managed according to the following guidelines and [Table \(8.11.1\) 1](#):

- Levels of electrolytes (potassium, total calcium, and magnesium) should be checked, and supplementation given to correct any values outside the normal range.
- Concomitant therapies should be reviewed and adjusted as appropriate for medications with known QT prolonging effects.

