Appendix 6: Prohibited Concomitant Medications

Prohibited medications and certain foods are not allowed in this study while subjects are receiving study drug.	
Strong CYP3A Inducers	CYP3A Substrates with a Narrow Therapeutic Window
Avasimibe, carbamazepine, enzalutamide, mitotane, phenytoin, rifampin, rifabutin, St. John's wort	Alfentanil, astemizole ¹ , cyclosporine, dihydroergotamine, ergotamine, fentanyl, pimozide, quinidine, everolimus, sirolimus, tacrolimus, terfenadine ¹

Note that this is not an exhaustive list. For an updated list, see the following link:
<http://www.fda.gov/Drugs/DevelopmentApprovalProcess/DevelopmentResources/DrugInteractionsLabeling/ucm080499.htm>

“CYP substrates with a narrow therapeutic window” refers to drugs whose exposure-response relationship indicates that small increases in their exposure levels by the concomitant use of CYP inhibitors may lead to serious safety concerns (eg, Torsades de Pointes).

¹ Withdrawn from the United States market because of safety reasons.

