Appendix 10: Examples of Strong and Moderate CYP3A4 Inhibitors

Moderate CYP3A4 Inhibitors
Aprepitant, cimetidine, ciprofloxacin, clotrimazole, crizotinib, cyclosporine, dronedarone, erythromycin, fluconazole, fluvoxamine, imatinib, tofisopam, verapamil
Strong CYP3A4 Inhibitors
Boceprevir, clarithromycin, conivaptan, grapefruit juice, indinavir, itraconazole
Ketoconazole, lopinavir/ritonavir, mibefradil, nefazodone, neflunavir, posaconazole
Ritonavir, saquinavir, telaprevir, telithromycin, voriconazole

Note: Based on FDA guidelines; Investigators should follow local institutional guidelines, where appropriate.

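### The protocol's only grapefruit instruction depends on taking tablets with food, and the two references for CYP3A4 inhibitors point to the wrong appendix

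*Protocol*

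**What the plan says.** **Grapefruit.** Protocol Section 4.3.5 allows dosing with or without food and then states that "if ivosidenib tablets are taken with food, the subject should avoid grapefruit or grapefruit products and avoid consuming a high-fat meal". Section 6.1 confirms that fasted dosing is acceptable: both tablets are taken "at the same time, preferably in the morning, in fasting or non-fasting conditions". The only other mention of grapefruit is in Appendix 10, whose strong-inhibitor list begins "Boceprevir, clarithromycin, conivaptan, grapefruit juice, indinavir, itraconazole".

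**Inhibitors and QTc.** Section 6.3.4 says that ivosidenib concentrations rise with "co-administration of a strong or moderate CYP3A4 inhibitor ([Appendix 6](#)), and increased ivosidenib plasma concentrations may increase the risk of QTc prolongation". It asks sites to consider alternatives and, where an inhibitor cannot be avoided, to monitor for QTc prolongation. Section 6.3.2 says: "Systemic administration of moderate or strong CYP3A4 inhibitors ([Appendix 6](#)) requires careful monitoring of the QTc". Section 8.11.1 gives the same advice without naming an appendix: "Systemic administration of a moderate or strong CYP3A4 inhibitor requires careful monitoring of QTcF".

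**Appendix 6.** Its header reads "Prohibited medications and certain foods are not allowed in this study while subjects are receiving study drug". Its two columns are strong CYP3A inducers and CYP3A substrates with a narrow therapeutic window. A note adds: "Note that this is not an exhaustive list".

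**The concern.** The food condition suits the high-fat-meal rule, which concerns what is eaten with the tablet. It does not suit a CYP3A4 inhibitor, because Section 6.3.4 describes the inhibitor effect without reference to food. Putting both rules under one condition leaves grapefruit only partly addressed.

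The wrong references compound this. An investigator who wants to know what counts as a moderate or strong inhibitor is sent to a list of inducers and substrates, and will not learn from it that grapefruit juice is classed as strong.

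What is at stake is prevention of a known risk: Section 2.4 names QT prolongation as an important identified risk of ivosidenib in all indications. The statistical analysis is not touched.

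**Working it through.** No sample size, power or event figure is involved. The check compares the relevant texts and counts entries.

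**1. Scope of the grapefruit sentence.** It can be read in two ways.

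| Reading of Section 4.3.5 | Who or what is left without an instruction |
|---|---|
| Applies only to subjects who dose with food | Subjects who dose fasting, as Sections 4.3.5 and 6.1 permit (number not stated) |
| Applies only to what is eaten with the tablet (the more natural reading) | Grapefruit eaten away from the dose, for all of the approximately 10 subjects |

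Instructions to subjects that name grapefruit: 1. Of these, instructions that cover the whole treatment period: 0.

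**2. The protocol's own pharmacology.** Appendix 10 classes grapefruit juice as a strong inhibitor. Section 6.3.4 connects strong or moderate inhibitors with higher ivosidenib concentrations and possible QTc prolongation. Neither text sets a food condition, so the condition in Section 4.3.5 has no stated basis where grapefruit is concerned.

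**3. The references.**

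| Place | Appendix cited for CYP3A4 inhibitors |
|---|---|
| Section 6.3.2 | Appendix 6 |
| Section 6.3.4 | Appendix 6 |
| Section 8.11.1 | none |

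Contents of the two appendices:

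- Appendix 6: 8 strong inducers + 12 narrow-window substrates = 20 entries, with no inhibitor list.
- Appendix 10: 13 moderate + 17 strong = 30 inhibitors, with grapefruit juice among the 17.
- Entries in both: 1 (cyclosporine), which Appendix 6 lists as a substrate.

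So 2 of 2 inhibitor references point to the wrong place. Appendix 10 appears only in the list of appendices and at its own heading; body sections that cite it: 0. Section 6.3.4 also cites Appendix 6 for strong inducers and for narrow-window substrates, and those references are correct.

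**4. Monitoring.** Under Table (4.1.2) 2 and Section 8.2.3, ECGs are scheduled on Days 1, 8, 15 and 22 of Cycle 1 and then on Day 1 of each 28-day cycle, whatever the subject eats. The gap is therefore in prevention and not in scheduled monitoring.

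**5. Size of effect.** The documents give no change in exposure or QTc for grapefruit, so none is estimated. The 129-hour half-life in Section 2.3.1.2 describes elimination of ivosidenib. It does not show what grapefruit eaten away from a dose would do, and it is not used here.

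**The case against.** The wrong references are hard to dispute. The case on the other side concerns grapefruit.

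- **Appendix 6 already bans certain foods during treatment.** Its header has no with-food condition, and grapefruit is the only specific food the protocol says to avoid, apart from high-fat meals. Read together, the two texts suggest avoidance throughout treatment. This has some force, but the header names no food, the table has no inhibitor category, and a site would have to infer the rule. Because the list is declared not exhaustive, its silence on grapefruit is not held against it; equally, it does not supply the instruction.
- **Section 6.3.4 covers any inhibitor.** If grapefruit juice counts as an inhibitor for the risk, it should count for the monitoring advice too. That is fair, and it softens the gap. But the advice concerns QTc monitoring, sits in a section on drug-drug interactions, and gives subjects no dietary rule.
- **An unconditional ban would be stricter than the rule for inhibitor drugs.** Those may be used with monitoring when unavoidable. The observation is correct, but a drug may be medically necessary and grapefruit is not. Section 4.3.5 already tells some subjects to avoid it, so the change extends an existing instruction.
- **Subjects may be told more elsewhere.** The consent form and the dosing diary (Section 6.4) could contain a full instruction, and Appendix 10 defers to local institutional guidelines where appropriate. This stands, and it limits the point to the protocol's wording.

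**Conclusion.** Both parts hold. The single grapefruit instruction does not cover the whole treatment period on either reading, and both references given for CYP3A4 inhibitors lead to an appendix without an inhibitor list.

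The reference error is a matter of fact. How far the grapefruit gap reaches depends on the reading: all of the approximately 10 subjects for grapefruit eaten away from the dose, or an unstated number who dose fasting. The conclusion rests on the protocol text alone, and no actual harm or failure to inform subjects is shown.

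The point is minor. It is worth correcting because it concerns operative safety instructions on an identified risk. Power, the primary endpoint and its analysis do not change.

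**What to change.** 1. Reword the sentence in Section 4.3.5, for example: *Subjects should avoid grapefruit and grapefruit products throughout ivosidenib treatment, whether or not tablets are taken with food. If tablets are taken with food, a high-fat meal should be avoided.*
2. In Sections 6.3.2 and 6.3.4, change the reference for CYP3A4 inhibitors from Appendix 6 to Appendix 10. Leave the inducer and substrate references to Appendix 6 unchanged.
3. Optionally, name grapefruit in Appendix 6 among the foods not allowed.

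The cost is one sentence and two references at the next amendment. If subject instructions repeat Section 4.3.5, the new sentence should be carried into them. The SAP needs no change.

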4.4. Discontinuation of the study or temporary halt

4.4.1. Premature discontinuation of the study or temporary halt

After having informed the Investigator, this study may be temporarily halted or prematurely discontinued at any time for any sufficient reasonable cause by the Sponsor or by the Institutional Review Board (IRB)/Independent Ethics Committee (IEC) or by the Competent Authorities.

Two copies of the written confirmation will be dated and signed by the Investigator. The IRB/IECs and Competent Authorities will be informed according to local regulations.

If the study is prematurely discontinued for reasons other than safety, subjects who are receiving treatment at the time the study is discontinued may remain on IMP if they are clinically benefiting. Subjects may receive nivolumab up to a maximum of 24 months. Ivosidenib may be continued for as long as the subject is receiving clinical benefit. Under some circumstances, the Investigator may be informed of additional procedures to be followed to ensure that adequate consideration is given to the protection of the subject's interests.

If the study is prematurely discontinued, the on-going participants should be seen as soon as possible and the same assessments as described in [Section 5.5](#) should be performed.

Under some circumstances, the Investigator may be informed of additional procedures to be followed to ensure that adequate consideration is given to the protection of the participant's interests.

In case of study temporary halt, the study may resume once concerns about safety, protocol compliance, and data quality are addressed and satisfy the Sponsor, following approval from the IRB/IEC and/or Competent Authorities, according to local regulations.

4.4.2. Premature discontinuation of the study in an Investigator site (early site closure)

The Sponsor reserves the right to close a study site at any time for any sufficient reasonable cause at the sole discretion of the Sponsor.

The Investigator may also initiate study-site closure at any time, provided there is reasonable cause and sufficient notice is given in advance of the intended termination.

Reasons for the early closure of a study site by the Sponsor or Investigator may include but are not limited to:

- Failure of the Investigator to comply with the protocol, the requirements of the IRB/IEC or local Competent Authorities, the Sponsor's procedures, or GCP guidelines.
- Inadequate recruitment of participants by the Investigator.
- Discontinuation of further study intervention development.

The IRB/IEC(s) and Competent Authorities will be informed according to local regulations.

